### **Research Synopsis**

This open-label pilot study aims to establish the safety of an accelerated intermittent theta burst stimulation (aiTBS) transcranial magnetic stimulation (TMS) protocol in patients experiencing mania or hypomania. aiTBS is an accelerated repetitive transcranial magnetic stimulation (rTMS) protocol in which 10 sessions of intermittent theta burst stimulation (iTBS) rTMS are given each day over five consecutive days. 30 participants will receive aiTBS over the right dorsolateral prefrontal cortex (DLPFC) with the Magventure MagPro X100 rTMS system. Their responses to the treatment will be measured with assessments measuring manic symptoms (Young Mania Rating Scale [YMRS], Altman Self-rating Mania Scale [ASRM], psychosis (Brief Psychiatric Rating Scale [BPRS]), depression (Montgomery-Asberg Depression Rating Scale [MADRS]), and overall mental illness (Clinical Global Impression scale-Severity [CGI-S] and CGI-improvement [CGI-I]). Electroencephalography (EEG) will also be employed to measure resting EEG response to aiTBS and effective cortical connectivity via TMS-evoked potential (TEP) response. Heart rate variability (HRV) is another potential biomarker of mania/hypomania and has been used as a measure of TMS responsiveness in depression (Iseger *et al.*, 2017, 2021). HRV monitoring will be employed here to investigate this variable in mania as well. Participants will be treated until they become euthymic, as measured by YMRS <7 or up to 5 days, whichever comes first. Our hypothesis is that this treatment will be well-tolerated by participants and few to no serious adverse events (SAEs) will occur.

### **Background and Significance**

Approximately 4.8% of adults will have a bipolar episode each year (Merikangas *et al.*, 2011; Miller, Dell'Osso and Ketter, 2014), and standard of care pharmacotherapies have relatively high rates of treatment resistance (Gitlin, 2006). This study is motivated by recent findings in the neuromodulation field suggesting that high-frequency (HF) rTMS (20 Hz) over the right DLPFC can treat symptoms of acute mania/hypomania in bipolar disorder (Grisaru *et al.*, 1998; Saba *et al.*, 2004; Praharaj, Ram and Arora, 2009; Tee and Au, 2020). An early double-blind controlled trial demonstrated the right DLPFC was superior to the left in treating mania in 16 patients (Grisaru *et al.*, 1998). A second open-label study in 8 patients confirmed that HF-rTMS over the right DLPFC reduced symptoms of mania (Saba *et al.*, 2004). A 41 patient single-blind randomized sham-controlled study further supported this work demonstrating that HF-rTMS over the right DLPFC was a well-tolerated and decreased measures of mania compared to the sham group (Praharaj, Ram and Arora, 2009). In these trials, patients were treated with standard of care pharmacotherapy plus rTMS as with this trial.

Other recent findings in neuromodulation have demonstrated the effectiveness of accelerated rTMS, TBS, and accelerated TBS protocols in mental illness. For example, sham-controlled trials of accelerated protocols in depression have demonstrated safety, tolerability, and efficacy (Baeken *et al.*, 2013, 2014, 2015). Further, iTBS has demonstrated equivalent efficacy to FDA-approved HF-rTMS protocols in depression (Li *et al.*, 2014; Blumberger *et al.*, 2018). Lastly, accelerated iTBS (aiTBS) such as aiTBS has not only proven safe and tolerable, but has also demonstrated higher response and remission rates for treating depression (Williams *et al.*, 2018; Cole *et al.*, 2020). These developments motivate the use of this novel and efficacious protocol, aiTBS, in treating other mental illnesses.

This is the first clinical trial investigating the application of aiTBS in bipolar disorder. The rationale for the use of aiTBS over the right DLPFC to treat mania is based on the safety, tolerability, and effectiveness of HF-rTMS over the right DLPFC in mania/hypomania (Grisaru *et al.*, 1998; Saba *et al.*, 2004; Praharaj, Ram and Arora, 2009), and the safety, tolerability, and efficacy of aiTBS in treating depression (Williams *et al.*, 2018; Cole *et al.*, 2020). Additionally, two cases applying conventional daily iTBS for the treatment of mania demonstrated efficacy (Muir *et al.*, 2018). We expect this study to demonstrate safety, tolerability, and efficacy in treating mania and to motivate larger sham-controlled trials in the future.

**Public Health Impact:** Completion of the proposal will provide evidence supporting a safe, tolerable, and effective treatment in a high-risk group of psychiatric inpatients. RTMS will be administered on the inpatient psychiatry unit during acute illness: a time point that is both practical and generalizable. This treatment has the potential to shorten manic episodes and hospital stay, but may also provide enduring effects that prevent future episodes of bipolarity. That is, a rapid-acting anti-mania treatment would reduce overall healthcare costs by decreasing length of stay and readmission rates.

**Preliminary data:** We recently completed our outpatient RCT using aiTBS in which we randomized 32 participants with highly treatment resistant depression (TRD; Maudsley Staging Method score  $\geq 7$ ) and treated 29 subjects. Two subjects withdrew before starting and one subject was excluded after being determined to not meet inclusion/exclusion criteria. We observed an extremely high rate of overall remission of depression where 86% of individuals experienced remission at some point during the 4 week followup period in the active group (12/14, MADRS $\leq 10$ ) versus a very low rate of remission in the sham group (13%; 2/15). We found an average reduction of 66% in depression symptoms (MADRS) immediately after aiTBS in the active group vs. 6% in the sham group. 10/14 participants showed  $\geq 50\%$  reduction in symptoms in active versus 2/15 in sham and 8/14 (57%) remitting from depression after 5 days of aiTBS in active versus 0/15 in sham, despite having failed numerous medications and psychotherapy. We followed these individuals for 4 weeks and there was a median 65-82% reduction in the MADRS during this period. At one month post-aiTBS, 64% of active-group participants continued to be responders and 43% were still in full remission, despite being 1 month after the last treatment. Mean MADRS remained significantly lower than baseline at the one-month follow up. These results provide substantial evidence that aiTBS is a safe, rapid-acting, and enduring treatment for mental illness. The outcomes of aiTBS for depression motivate us to explore the safety, tolerability, and efficacy of aiTBS in other applications such as mania.

**The Effects of rTMS on right DLPFC in mania:** RTMS over the right DLPFC has demonstrated safety, tolerability and efficacy in treating the symptoms of mania (Grisaru *et al.*, 1998; Saba *et al.*, 2004; Praharaj, Ram and Arora, 2009; Pathak, Sinha and Praharaj, 2015). Further, two published cases have demonstrated efficacy of iTBS protocols in treating mania (Muir *et al.*, 2018). These trials applied a conventional daily rTMS treatment schedule. Our aiTBS protocol is unique in that it applies a higher-dosage of rTMS with consideration of a modern understanding of spaced learning (Smolen, Zhang and Byrne, 2016; Etkin *et al.*,

2019) and advanced targeting (Williams *et al.*, 2018). This accelerated form of iTBS allows for the possibility to treat acute mania in the inpatient hospital setting.

**Important to the present study:**

**Objectives**

**Primary objective**

1. To assess the safety and feasibility of active aiTBS in hospitalized patients with bipolar disorder I and II as defined by adverse events and study retention rates (measured as actual recruitment/recruitment milestones).

**Secondary objective:**

1. To determine the preliminary anti-manic efficacy of active aiTBS in hospitalized patients with bipolar disorder I and II as measured by a significant reduction in the Young Mania Rating Scale (YMRS) from baseline to the immediate post-treatment visit.

**Exploratory objectives:**

1. To determine the preliminary anti-manic efficacy of active aiTBS in hospitalized patients with bipolar disorder I and II as measured by a significant reduction in the Altman Self-rating Mania Scale (ASRM) from baseline to the immediate-post treatment visit.
2. To determine if higher cortical response to TMS (as measured by resting EEG and TMS-EEG at baseline and immediate-post visit) is correlated with the anti-manic effects of aiTBS as measured by baseline, daily, and immediate post YMRS assessments.
3. To determine if an increase in HRV (as measured with a Neuroconn device) from baseline to the immediate-post visit is correlated with the anti-manic response to aiTBS as measured by baseline, daily, and immediate post YMRS assessments..
4. To determine the functional connectivity changes in the brain as measured by resting-state functional MRI from baseline to immediate-post treatment visit following an aiTBS intervention over the right DLPFC in inpatients with bipolar disorder I and II experiencing symptoms of mania.

**Study Design/Methodology**

**Phase:** This is a Phase II clinical trial.

**Trial Design:** open-label

**Methods to minimize bias:** This study will minimize bias via its inclusion and exclusion criteria and the use of validated laboratory and interview/self-report measures. Explicit hypotheses and corresponding planned statistical analyses, power estimates, careful consideration of potential confounds. All experimental details will be reported in a fully transparent manner to support replication.

**Dose Escalation:** TMS stimulation dose will be individually determined according to 90% rMT plus depth correction, and then the aiTBS protocol will be administered with a consistent dose across all participants receiving active stimulation of 18,000 pulses/day and 90,000 pulses/course.

**Study Arms:** One arm, active open-label

**Site(s):** Single Site (Department of Psychiatry & Behavioral Sciences, Stanford University)

**Name of Study Intervention:** Accelerated theta burst stimulation for inpatients with bipolar disorder

**Interim Analysis:** N/A

**Stratification:** None planned.

### **Study Population**

We will enroll 30 participants in this open-label active Phase II Trial. The target population is adults of all genders and ethnicities who are between 18 and 80 years of age with bipolar affective disorder I or II and who are otherwise in good general health. Participants must be without contraindications to Magnetic Resonance Imaging (MRI) or transcranial magnetic stimulation (TMS) and must be able to attend all study visits.

### **Inclusion Criteria**

In order to be eligible to participate in this study, an individual must meet all of the following criteria:

1. Male or female, between the ages of 18 and 80 years at the time of screening.
2. Able to read, understand, and provide written, dated informed consent prior to screening. Proficiency in English sufficient to complete questions and follow instructions during fMRI assessments and aiTBS interventions
3. Stated willingness to adhere to all study procedures, including availability for the duration of the study, and to communicate with study personnel about adverse events and other clinically important information
4. **Primary diagnosis of Bipolar I or II Disorder** according to the Diagnosis and Statistical Manual of Mental Disorders, 5th edition (DSM-5)
5. Currently experiencing a **hypomanic or manic episode** according to the criteria defined in the Diagnosis and Statistical Manual of Mental Disorders, 5th edition (DSM-5)
6. **YMRS score of  $\geq 12$**  at screening.
7. Access to ongoing psychiatric care after completion of the study.
8. Must be adherent or agreeable to pharmacotherapy per clinical standard of care at screening.
9. Patients who are in both voluntary and involuntary hold.
10. In good general health, as evidenced by medical history.
11. For females of reproductive potential: use of highly effective contraception.

### **Exclusion Criteria**

1. Currently **pregnant or breastfeeding**.

2. Primary psychiatric condition **other than Bipolar I or II Disorder requiring treatment** other than stable comorbid anxiety disorder.
3. Diagnosis of Intellectual Disability or Autism Spectrum Disorder
4. Current **moderate or severe substance use disorder** or demonstrating signs of **acute substance intoxication or withdrawal**
5. **Active suicidal ideation** (defined as an M-SSI > 8)
6. History of **significant neurologic disease**, including dementia, Parkinson's or Huntington's disease, brain tumor, seizure disorder, subdural hematoma, multiple sclerosis, or history of significant head trauma
7. Contraindication to receiving rTMS (e.g., metal in head, history of seizure, known brain lesion)
8. Contraindication to MRI (e.g. ferromagnetic metal in their body)
9. Treatment with another investigational drug or other intervention within the study period
10. Any other condition deemed by the PI to interfere with the study or increase risk to the participant
11. Current unmanageable psychosis that the PI believes would interfere with treatment
12. Any history of psychosurgery
13. Depth-adjusted aiTBS treatment dose > 65% maximum stimulator output (MSO).
14. Any other condition deemed by the PI to interfere with the study or increase risk to the participant.

The effects of rTMS on the developing human fetus are largely unknown (Eryilmaz *et al.*, 2015). Accordingly, we will not be enrolling pregnant women to this study. Women of childbearing potential must agree to use adequate contraception (hormonal / barrier method of birth control or abstinence) prior to study entry and for the duration of study participation. Females of childbearing-age will have a pregnancy test prior to starting the rTMS stimulation course. Should a woman become pregnant or suspects she is pregnant while participating in this study, she should inform study staff.

Participants taking certain psychoactive medications will be assessed for safety by the PI, due to potential for increase of seizure risk (Pisani *et al.*, 2002) and change in cortical excitability (Minzenberg and Leuchter, 2019).

Individuals older than 80 years of age will be excluded for the following reasons:

1. Even though the study depth adjusts individuals with greater prefrontal over primary motor cortex atrophy, the safety limit is at 120% and some individuals require greater than 120% depth adjustment to reach PFC (Kozel *et al.*, 2000; Sabesan *et al.*, 2015). With this, there is evidence of reduced efficacy in those individuals with advanced age (Freitas *et al.*, 2011; Abellaneda-Pérez *et al.*, 2019).
2. There is evidence of reduced plasticity in individuals with advanced age with a reduction in the duration of the effects of TBS (Freitas *et al.*, 2011; Abellaneda-Pérez *et al.*, 2019) which may impact the response to the approach.

### **Study Interventions:**

**Active aiTBS Intervention:** We have previously discussed this stimulation approach with the FDA and the FDA deemed the approach nonsignificant risk (NSR). aiTBS will be delivered similarly to previous aiTBS studies (Williams *et al.*, 2018; Cole *et al.*, 2020) using the MagVenture MagPro X100 (Skovlunde, Denmark) TMS device equipped with a Cool-B65 A/P coil or Cool D-B80 A/P coil. The right DLPFC target will be

localized for each participant via Montreal Neurological Institute (MNI) coordinates applied to a T1 structural MRI using a Localite TMS Navigator (Siddiqi *et al.*, 2020). The right dorsomedial (DM) PFC is an emerging potential TMS target in bipolar disorder that may provide mood stabilization. This region may be targeted in this study if an anti-manic response to the previously mentioned DLPFC target is not observed. Baseline and immediate-post YMRS scores will be used to measure anti-manic response. Participants will be treated with 1,800 pulses of iTBS (3-pulse 50-Hz bursts at 5-Hz for 2-second trains, with trains every 10 seconds) per session at 90% resting motor threshold and depth-adjustment to the MNI target (Nahas *et al.*, 2004). Each session will last 10 min followed by a 50-minute intersession interval. Ten sessions will be applied per day (18,000 pulses/day) for 5 consecutive days (90,000 total pulses).

**Dosing and administration:** We will deliver only active aiTBS intervention via a MagPro X100 (MagVenture, Skovlunde, Denmark) TMS. The intervention paradigm consists of 10 daily sessions (50 total over 5 days) of intermittent theta-burst (iTBS) stimulation (3-pulse 50-Hz bursts at 5-Hz for 2-second trains, with trains every 10 seconds), delivered with 50-minute inter-session intervals (10-minute sessions, 50-minutes in between sessions). Stimulation will be delivered at 90% of the resting motor threshold (with depth correction to account for the distance between the scalp and cortex). aiTBS protocol will be administered with a consistent dose escalation across all subjects of 18,000 pulses/day and 90,000 pulses/course. If participants meet remission criteria before treatment day 5 as measured by daily YMRS, participants will not receive further treatments.

The right DLPFC will serve as the target for stimulation, though DMPFC may also be targeted if this initial target does not demonstrate efficacy. The intervention target will be located via a Localite TMS Navigator. The treater identifies the target in the manner approved by the FDA for the Localite TMS Navigator device.

### **Study Schedule:**

Assessment	Visit 1	Visit 2*	Visit 3-7	Visit 8
	Screening	Baseline	Treatment Days	Immediate Post
Capacity to Consent	x			
Screening Informed Consent	x			
Demographics	x			
MRI Safety Screening Form	x			

TASS	x			
Medical and Psychiatric History	x			
Urine Analysis	x			
Inclusion/Exclusion Criteria	x			
MINI	x			
SCID Overview	x			
MSSI	x			
YMRS**		x	x	x
BPRS		x	x	x
CGI		x	x	x
ASRM		x	x	x
MADRS-S		x	x	x

Current Medications		x	x	x
Motor Threshold		x	x	
Enrollment/ Randomization		x		
Adverse Events			x	x

Procedures	Visit 1 Screening	Visit 2 Baseline	Visits 3-7 Treatment Days	Visit 8 Immediate Post
Obtain MT	x	x	x	
Stimulation log (rTMS)			x	
Resting EEG		x		x
TMS-EEG		x		x
T1 MRI		x		x
Resting state fMRI		x		x
HRV		x	x	x

\*for this inpatient TMS study, the screening and baseline visits could occur at the same time and place if the potential participant qualifies for the study

\*\*A YMRS score of  $\geq 12$  is an inclusion criteria for this study. If this score falls below 12 after the participant has been enrolled then the YMRS score will be measured every third treatment, as opposed to once per day, for closer monitoring of manic symptoms. If the YMRS score falls below 7, this will be recorded as remission and the TMS treatment will end.

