**Table 3: Adverse events**

AEs will be systematically assessed at the start and end of every study day and will be assessed via the following standardized questions that will be asked by research staff:

- Have you had any difficulty with the study interventions?
- Have you had any problems or other things bothering you since our last visit?
- Has anything bothered you enough to...
  - ...prevent you from doing anything you had planned?
  - ...take a prescription or over-the-counter medication or supplement?
  - ...see a medical professional?
  - ...modify the treatment of a pre-existing medical condition?

Any positive response(s) to the above questions will be documented electronically as part of an AE form on REDCap. Any documented AE will be asked about at each subsequent AE assessment until it resolves or through the time frame specified above. In Table 3 above, there is a list of common AEs (Blumberger *et al.*, 2018). If an unexpected AE occurs, or if a common AE occurs with severity greater than that expected, the participant will be further evaluated by a member of the study team with formal medical training.

In addition, although the risk of TMS-induced mania is low (Tee and Au, 2020), it will be monitored using the YMRS scale as a solicited event. The scale will be administered at baseline, before each treatment day, and the immediate-post visit. The score will be monitored along with input from the inpatient clinical team concerning possible worsening of symptoms.

Research staff will be trained to attend to signs of AEs and to report any potential unrelated or unexpected AE immediately to the Protocol Director (PD) [name]. If AEs occur, appropriate medical and/or

psychiatric care will be facilitated for the research participant, and recorded in the appropriate electronic AE logs on REDCap. As per Stanford IRB requirements, AEs will be reported to the IRB annually. The NIMH Program Officer will be informed of any actions taken by the IRB as a result of any AEs within 7 business days of notification by the IRB (e.g. study modifications imposed by the IRB).

All subjects will have telephone and email contact information to reach the Principal Investigator and the Stanford IRB, in case of any distress or adverse response to rTMS or other components of the study.

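### As scheduled, the YMRS score that qualifies a participant is also the efficacy baseline, and one exclusion appears to depend on an MRI taken after the only eligibility check

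*Combined protocol and SAP*

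**What the plan says.** Inclusion 6 (Inclusion Criteria) requires a "YMRS score of $\geq 12$ at screening". In the Study Schedule, the row "Inclusion/Exclusion Criteria" is ticked at Visit 1 (Screening) and nowhere else. The YMRS row is ticked at Visit 2 (Baseline), Visits 3–7 and Visit 8, with no tick at Visit 1. The adverse event text under Table 3 gives the same timing: "The scale will be administered at baseline, before each treatment day, and the immediate-post visit". The first schedule footnote allows the two early visits to be merged: "the screening and baseline visits could occur at the same time and place if the potential participant qualifies for the study".

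The secondary objective is preliminary anti-manic efficacy "as measured by a significant reduction in the Young Mania Rating Scale (YMRS) from baseline to the immediate post-treatment visit". Study Interventions uses the same pair of readings: "Baseline and immediate-post YMRS scores will be used to measure anti-manic response".

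Exclusion 13 (Exclusion Criteria) reads "Depth-adjusted aiTBS treatment dose > 65% maximum stimulator output (MSO". Study Interventions places the stimulation target on a T1 structural MRI and adjusts the dose for depth to that target. T1 MRI is first ticked at Visit 2, as is enrolment, and their order within the visit is not given. Motor threshold, the other component of the dose, is ticked from Visit 1 in the Procedures table but only from Visit 2 in the Assessment table.

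**The concern.** Two items needed to decide eligibility are first scheduled after the only eligibility check.

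For YMRS this has a statistical consequence. If the Visit 2 score decides entry, participants whose error on that day happened to be upward are more likely to pass the cut-off of 12. Their next reading is then expected to be lower even if nothing has changed. The trial has one arm, so no control group shows how much of the observed fall has this origin. Hypomanic episodes and Bipolar II disorder are eligible, so scores near 12 are plausible.

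For exclusion 13 the consequence is procedural. Someone may be found ineligible at Visit 2, and the plan does not say whether that person is a screen failure or an enrolled participant.

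**Working it through.** **1. Visit order.**

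| Item | Needed for | First ticked |
|---|---|---|
| Eligibility check | All criteria | Visit 1, once |
| YMRS | Inclusion 6, and efficacy baseline | Visit 2 |
| Motor threshold | Exclusion 13 | Visit 1 or Visit 2, depending on the table |
| T1 MRI | Exclusion 13 (inferred) | Visit 2 |
| Enrolment | – | Visit 2, order not given |

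Both the schedule and the Table 3 text start YMRS at baseline. On the schedule as written, the Visit 2 score is therefore the only one that can satisfy inclusion 6.

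**2. Size of the artefact.** There is no figure in the plan to reproduce: it gives no YMRS mean, SD, reliability or effect size, and no derivation of N = 30.

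- From the documents: cut-off 12, n = 30, two-sided 0.05 (so 2.5% in the direction of a reduction), single arm.
- Assumed: mean YMRS of those assessed 14, 20 or 24; SD of observed scores 5–8; test-retest correlation r 0.6–0.9; normal scores.

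With a = (12 − mean)/SD, the expected fall with no true change is

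fall = (1 − r) × SD × φ(a) / [1 − Φ(a)].

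Worked case, mean 14, SD 6, r = 0.75: a = −0.333, φ(a) = 0.377, 1 − Φ(a) = 0.631, ratio 0.598. The fall is 0.25 × 6 × 0.598 = 0.90 points.

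The chance of a false significant reduction comes from simulating a paired t-test at n = 30 with no true change and measurement error only. The paired test stands in for the mixed model in the Statistical Analysis Plan. Simulation error is up to about one percentage point.

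| Mean | SD 5, r 0.9 | SD 5, r 0.6 | SD 8, r 0.9 | SD 8, r 0.6 | False reduction over the whole range (nominal 2.5%) |
|---|---|---|---|---|---|
| 14 | 0.28 | 1.12 | 0.52 | 2.07 | about 10–37% |
| 20 | 0.06 | 0.23 | 0.23 | 0.92 | about 3–11% |
| 24 | 0.01 | 0.05 | 0.11 | 0.44 | about 3–5% |

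The error-only rates are the harsher case. In the worked case the rate is about 21% with error only, and about 11% if individual true change also varies with SD 5 around zero.

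**3. Effect of a separate baseline.** If one reading qualifies the participant and a later one with independent error is the baseline, the expected artefact is about 0 and the false-reduction rate returns to about 2.5% in every setting. If a fraction s of the error variance is shared between the two readings, the remaining artefact is s times the original. In the worked case, s = 0.5 leaves 0.5 × 0.90 = 0.45 points and s = 0.8 leaves 0.8 × 0.90 = 0.72. Two interviews on one day therefore give less protection than readings on different days.

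**The case against.** The strongest reply is that inclusion 6 itself names screening, so a screening YMRS may be intended and the missing Visit 1 tick may be a slip in the table. That stands as far as it goes: a reader might infer that double use of the score is established, and the documents do not establish it. They establish that the Inclusion Criteria conflict with the Study Schedule and the Table 3 text, and that following the latter two produces double use. The passages need reconciling either way.

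Second, another pre-treatment reading is already planned, because YMRS is due before each treatment day. This is correct and makes the repair cheaper, but the plan does not name that reading as the baseline.

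Third, YMRS reduction is a secondary, preliminary endpoint in an uncontrolled pilot on concurrent pharmacotherapy. Regression to the mean is only one source of a non-specific fall, and removing it leaves the comparison uncontrolled. This limits the importance of the point but does not remove it.

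On exclusion 13, that depth is read from the T1 scan is a reasonable inference and not an explicit statement. A reader might also infer that ineligible people would be stimulated. The schedule does not support that, since treatment starts at Visit 3.

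Finally, a reader might infer that three exclusions at Visit 2 would defeat the primary hypothesis, because 27/30 is exactly 90% and the hypothesis requires more. The documents do not support this. The primary objective measures retention as actual recruitment against recruitment milestones, and the primary hypothesis sets it against anticipated recruitment, so a replaced participant need not lower it. The order of MRI and enrolment at Visit 2 is not stated, and screen failures are logged separately (Documentation of Signed Consent).

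**Conclusion.** The inconsistency is real and minor. Followed as scheduled, the qualifying YMRS is the efficacy baseline, and the bias runs only toward apparent benefit. Under the stated assumptions (SD 5–8, correlation 0.6–0.9) it is about 0.3–2.1 points if those assessed average 14, about 0.1–0.9 at 20 and under 0.5 at 24. With no true change and error only, the corresponding chances of a false significant reduction are about 10–37%, 3–11% and 3–5%, against 2.5%. It matters if many participants score close to 12 and is negligible if most score well above it; the documents do not say which to expect. For exclusion 13, the conclusion is only that the final eligibility decision appears to fall after the only scheduled check. No effect on retention or on exposure to stimulation is shown.

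**What to change.** 1. Reconcile inclusion 6, the Study Schedule and the Table 3 text by scheduling the qualifying YMRS at Visit 1.
2. Name a separate, later, pre-treatment YMRS as the efficacy baseline in the secondary objective and the Statistical Analysis Plan. The reading already planned for treatment day 1, taken before the first session, can serve. It is the better choice when Visits 1 and 2 coincide, because same-day readings may share error.
3. Tick a final eligibility check at Visit 2, after MRI and motor threshold and before enrolment, and log people excluded there as screen failures. Align the two motor threshold rows and state where the depth measurement comes from.

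The cost is a schedule edit and a few sentences. Using the day 1 reading as baseline needs no additional baseline interview, although a YMRS at Visit 1 is one more interview than is now scheduled if Visit 2 keeps its own. The reported mean change becomes slightly less favourable, and some bias remains to the extent that the two readings share error.

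### YMRS change is counted from Visit 2, not from the last score before the first aiTBS session, so improvement before treatment is credited to aiTBS

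*Combined protocol and SAP*

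**What the plan says.** All references are to the combined protocol and SAP.

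- **Endpoint.** The Secondary objective measures YMRS reduction "from baseline to the immediate post-treatment visit". Study Interventions repeats this: "Baseline and immediate-post YMRS scores will be used to measure anti-manic response".
- **Visits.** The Study Schedule labels Visit 2 Baseline, Visits 3-7 Treatment Days and Visit 8 Immediate Post. YMRS is ticked at Visits 2 to 8 but not at Visit 1. Enrolment is a Visit 2 row. Screening and baseline may be combined.
- **Entry.** Inclusion Criteria require YMRS of at least 12 at screening. With no YMRS ticked at Visit 1, the schedule makes the Visit 2 score both the qualifying and the baseline score.
- **Readings on treatment days.** The text under Table 3 in Adverse Event Reporting says: "The scale will be administered at baseline, before each treatment day, and the immediate-post visit". Baseline is listed apart from the treatment-day readings, so a score before the first session is planned.
- **Remission rule.** The schedule footnote starts its monitoring rule at enrolment ("If this score falls below 12 after the participant has been enrolled then the YMRS score will be measured every third treatment") and continues: "If the YMRS score falls below 7, this will be recorded as remission and the TMS treatment will end". Study Interventions says: "If participants meet remission criteria before treatment day 5 as measured by daily YMRS, participants will not receive further treatments". The Research Synopsis says: "Participants will be treated until they become euthymic, as measured by YMRS <7 or up to 5 days, whichever comes first".
- **Setting.** There is one open-label arm (Study Design/Methodology), alongside standard pharmacotherapy (Background and Significance; Inclusion Criteria). The Statistical Analysis Plan defines neither an analysis baseline nor a minimum exposure for counting remission.

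**The concern.** A before-and-after change in a single arm has no control group to cancel improvement that comes from other causes. Here the reference score is taken a visit before treatment starts, in patients who are receiving or agreeing to antimanic medication. It is also the score on which they were selected. Two things can lower the YMRS before the first aiTBS session: true improvement, and regression to the mean after selection on an observed 12 or more. Both enter the endpoint as treatment effect, although the plan already collects the score that would separate them.

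The same Visit 2 score enters the exploratory EEG and HRV correlations, and the judgement of whether the first stimulation target shows a response.

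Remission has a smaller version of the problem. The rule carries no exposure requirement, so as written a participant below 7 at the reading before the first session could be recorded as a remission without having received aiTBS.

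**Working it through.** **1. The plan's own timing figure.** Study Timeline gives approximately 7 days from baseline to completion. Visits 2 to 8 are 1 baseline + 5 treatment + 1 post = 7 visit days, which agrees. Seven consecutive visit days have 6 intervals, so the Visit 2 to Visit 3 gap is nominally about one day, or one interval of six. The 7 days are approximate and no maximum gap is set.

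**2. What the endpoint contains.** Write Y2 for the Visit 2 score, Y3 for the score before the first session and Y8 for the post score. Then

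Y2 - Y8 = (Y2 - Y3) + (Y3 - Y8).

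The plan analyses the left side. Only the second bracket covers the treatment period.

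**3. Size of the first bracket.** The documents give no drift rate, SD or rating error, so every input here is an assumption.

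- Drift: 1-2 points per day × 1 day = 1-2 points. Each further day of gap would add the same again.
- Selection alone: simulated with mean true YMRS 16-25, between-person SD 6, rating-error SD 2-4, entry on an observed score of 12 or more, and no drift. The mean fall at re-scoring is 0.03 to 1.0 points.
- Drift of 1-2 points and selection together, same simulation: 1.03 to 2.99 points.

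**4. Effect on the significance test.** The SAP names no specific test for this endpoint beyond mixed models, so a paired t-test stands in (n = 30, two-sided 0.05). The mean fall that reaches p<0.05 is 2.045 × SD/√30:

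- SD 6: 2.24 points
- SD 8: 2.99 points
- SD 10: 3.73 points

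Now suppose aiTBS has no effect and nothing drifts after Visit 3. With noncentrality (mean fall/SD) × √30, the chance of p<0.05 is:

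| Pre-treatment mean fall | SD 6 | SD 8 | SD 10 |
|---|---|---|---|
| 0 | 0.05 | 0.05 | 0.05 |
| 1 | 0.14 | 0.10 | 0.08 |
| 2 | 0.42 | 0.26 | 0.19 |

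With the pre-session score as baseline, the first bracket drops out and, under these same conditions, the chance returns to 0.05.

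**5. Remission before treatment.** A participant at the entry minimum needs a fall of 12 - 6 = 6 points to read below 7. One day at 1-2 points takes 12 to 10-11, so drift alone does not get there; rating error or a large one-day fall is also needed. In the simulation with drift of 1-2 points, the chance per participant is 0.03% to 5.8%. By 1 - (1 - p)^30, the chance of at least one such participant in 30 is about 1% to 83%. That range shows only that the frequency cannot be known from the documents.

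**The case against.** The strongest reply is that little is at stake. A baseline visit before treatment is a usual reference point, efficacy here is preliminary and secondary, and the primary safety and retention objective does not use YMRS change. Medication, natural course and unblinded rating confound all five treatment days, so a later baseline removes about one interval of six and leaves the larger problem. This stands as a limit on importance. It does not defend the Visit 2 reference, because the better score is already planned.

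Inclusion Criteria also place the qualifying score at screening. If a separate screening YMRS were taken, Visit 2 would shed much of the regression to the mean. The schedule does not plan one, and drift after Visit 2 would remain in any case.

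Four stronger readings are tempting, and the documents do not support them:

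- **That up to 6 points could precede treatment, enough to produce remission by drift alone.** At 2 points per day this needs a three-day gap, which does not fit a total of about 7 days if the post visit follows promptly.
- **That the interval is free of stimulation.** Motor threshold and TMS-EEG at Visit 2 both deliver TMS pulses. The interval is free of aiTBS treatment only.
- **That the plan means to count remissions in untreated participants.** The wording about ending treatment, further treatments and treating until euthymic presupposes that treatment has begun. The text fails to exclude the case, probably by oversight, and remission rate is not a named objective.
- **That the daily scores go unused.** Exploratory objectives 2 and 3 use daily YMRS. The gap is that the secondary endpoint does not take the pre-session score as its reference.

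**Conclusion.** The concern holds in a limited form. The secondary endpoint credits aiTBS with any change between Visit 2 and the first session, and on the schedule its baseline is also the selection score. With a nominal gap of about one day, this is about 1-2 points at an assumed drift of 1-2 points per day, plus a simulated 0.03 to 1.0 points from selection. With 30 participants and an assumed SD of change of 8, a pre-treatment fall of 1-2 points raises the chance of a nominally significant result from 0.05 to 0.10-0.26 when aiTBS does nothing and nothing drifts later.

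The direction favours aiTBS when mania is resolving, and would reverse if patients worsened after Visit 2. The timing and the endpoint definition come from the documents; the drift, SD and rating error do not. The remission gap is real in the text but secondary, and its frequency cannot be estimated. The change is worth making because it costs very little, but it does not turn the single-arm change into an estimate of the aiTBS effect.

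**What to change.** On the analysis side:

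1. In the Secondary objective and the Statistical Analysis Plan, define the analysis baseline for YMRS change as the last YMRS before the first aiTBS session. Do the same for ASRM only if its treatment-day assessment is timed before the first session; the schedule ticks it on those days without a time.
2. Report the Visit 2 to pre-session change, with days elapsed, as a separate descriptive line. Over about one day in about 30 people it is a weak estimate of background drift, and should be labelled as such.
3. In any reported remission count, include only participants with at least one delivered aiTBS session. List separately anyone below 7 before the first session, and state how they enter the change analysis.

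Separately, the Research Synopsis, Study Interventions, the Study Schedule footnote and the YMRS text in Adverse Event Reporting should be reconciled on when the remission rule starts to apply. The footnote also governs the ending of treatment, so that is for the sponsor to settle; no clinical rule is proposed here.

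Cost: wording, with no new YMRS assessment, and a timing rule for ASRM if it is included. The mean fall and any remission count may look slightly less favourable. Confounding during treatment days 1-5 remains and should be stated as a limitation.
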